10.14. Foreseeable Complications

From the Manufacturer and User Facility Device Experience database, the common reported injuries from PAP therapy and associated interface use are pressure sores, leading to cuts, rashes, and skin abrasions and breakdown. Allergic reaction to materials in the interface can occur. Common complaints are discomfort and soreness on the areas of contact with the interface. Participants on the clinical investigation are informed that they can switch back to their usual mask if required. In instances of malfunction or damage, the investigational product and its components may be replaced, with this recorded in the CRF. In the event that participants require additional healthcare after they have been involved in this clinical investigation, and this medical attention is necessary because of the participant partook in the clinical investigation or differs from that normally expected as part of their usual healthcare or follow-up, the PI will be responsible for ensuring availability and access to appropriate healthcare. The investigation site will provide evidence of an emergency plan of action to F&P for any participants who required this additional healthcare.

11. Clinical Investigation Documentation

11.1. Case Report Form

Data from the clinical investigation will be recorded from source documents and transcribed to a CRF to enable the collection of participant data. [REDACTED]

11.2. Protocol Deviations

All deviations from the CIP shall be recorded in the CRF, with an explanation for the deviation. [REDACTED] Deviations shall be reported to F&P who is responsible for analyzing them and assessing their significance. The reasons for withdrawal and discontinuation of any participant from the investigation shall be recorded. If such discontinuation is related to the poor performance or safety of the investigational product, that participant will still be followed up with if possible. When and where relevant, ethics committees, competent authorities, or appropriate regulatory bodies will be informed about protocol deviations and protocol violations.

12. Statistical Considerations

12.1. Description of Statistical Design

The statistical design of this clinical investigation is aimed at evaluating the product requirements as defined by the respective [REDACTED] mask is safe and effective prior to its release into global markets and to support regulatory clearance applications where required. Therefore, the statistical design of this clinical investigation is considerate of its objectives and endpoints being confirmatory in nature, rather than exploratory, or in the pilot stage. [REDACTED]

[figure not shown]
Data from participant questionnaires and compliance reports will be saved in supporting folders of the [REDACTED] [REDACTED] For each participant and requirement, it will be determined if these have been met individually based on the acceptance criteria. Minitab will be used to perform a one-sided one-proportion test on each requirement using the corresponding confidence limit to confirm that the acceptance criteria has been met.

Details are as follows:

- H_0 : Proportion = Reliability Limit
- H_1 : Proportion > Reliability Limit
- Acceptance criteria: $P \leq 0.05$ to reject H_0

12.2. Pass and Fail Criteria

Below are the acceptance criteria for the product validation aspect of this clinical investigation, used to evaluate aspects of the investigational product, and that may be used as evidence to further develop areas where a poor result is observed. Any requirements relating to marketing claims are for observational purposes only, so will not have acceptance criteria. A summary of this information is provided in the corresponding [REDACTED]

12.3. Statistical Termination and Procedure Deviations

No interim analysis will be conducted as statistical outcomes will not change the conduct of the clinical investigation. Statistical procedure deviations will be reported to the PI and the sponsor. Deviations from the original statistical plan will be explained in the final study report, located in [REDACTED]

12.4. Selection Criteria

Data from all participants who use the investigational product as part of this clinical investigation will be included in the analysis, unless a clear reason for exclusion is present, such as definitive proof the participant was not using the investigational product during the intervention period. Any data points that are excluded will be documented clearly with the reason for their exclusion. For participants who have withdrawn, all data collected up to the point of withdrawal may be used in the analysis, provided the data is complete and accurate.

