5.4. Research Purpose

This clinical investigation is designed to validate and confirm the overall performance and acceptability of the [REDACTED] prior to its global commercial release, serving as the final pre-market assessment to ensure the investigational product, when used according to its intended purpose, provides positive airway pressure (PAP) therapy for existing patients which is equivalent to the treatment provided by their usual mask. Nasal pillows masks, such as the [REDACTED], are commonly used as part of PAP therapy, both in clinical settings and in-home environments for the treatment of various respiratory conditions, including obstructive sleep apnea (OSA). Currently, as per ISO-14155:2020, 'Annex I', the [REDACTED] is considered in the pivotal stage of device development.

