10.12. Withdrawal Criteria

Participants will be informed that they have the right to withdraw from the clinical investigation at any time, without prejudice or compromise to their medical care, and are not obliged to state their reasons. [REDACTED]

[REDACTED] Participants are informed that they can return to using their usual mask for PAP therapy during the clinical investigation if they have reason to do so. Withdrawal can occur in person at the investigation site, or by phone call or email. Upon withdrawal, the participant will be informed to immediately stop using the investigational product and to return all associated items and packaging to the investigation site at their earliest convenience. In the event of a participant being withdrawn during a scheduled or unscheduled visit at the investigation site, the investigational product will be retrieved from the participant. Thereafter, participants will no longer be considered active in the clinical investigation. If the PI elects to withdraw a participant, the same procedure for investigational product reconciliation will be followed, and where serious or emergent medical attention is required, the PI will follow the usual emergency code of practice instituted at the investigation site.

The PI may withdraw a participant at any time for the following reasons:

- Protocol violation
- Safety concerns
- Serious illness
- AEs

Data from withdrawn participants may be used when results of the clinical investigation are analyzed if it is complete and accurate. If data from withdrawn participants is not used, [REDACTED] Participants will not be replaced after all original recruits have been attended their first appointment at the investigation site. If participants withdraw before this, another participant can be recruited as a replacement.

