13.5. Expected Side Effects

Throughout the clinical investigation, participants may experience a poor night sleep with the investigational product as it will be different to the usual mask they use. These are disclosed in the ICF issued to participants and will be documented as expected side effects in the CRF, but not as AEs. Participants will be informed that these side effects are expected as a consequence of receiving PAP therapy, particularly when you initially begin use, and may subside over time with continued adherence to treatment. They will also be advised that if these side effects are unduly intrusive to their daily life or prevent them from using PAP therapy to manage the respiratory condition for which it was prescribed, to consult the PI or contact the investigation site. Alternatively, participants can switch back to using their usual mask for PAP therapy.

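### Section 12.4 allows exclusion for proven non-use whatever its cause, so a participant who stays enrolled but gives up the mask because of the mask can leave the denominator

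*Combined protocol and SAP*

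**What the plan says.** The default in section 12.4 is inclusion: "Data from all participants who use the investigational product as part of this clinical investigation will be included in the analysis". The exception is a clear reason for exclusion, and the only example given is "such as definitive proof the participant was not using the investigational product during the intervention period". The safeguard attached to it is "Any data points that are excluded will be documented clearly with the reason for their exclusion".

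Three other sections tell participants that they may stop using the mask without leaving the study:

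- 10.12: "Participants are informed that they can return to using their usual mask for PAP therapy during the clinical investigation".
- 10.14, next to a list of skin injuries and discomfort: "Participants on the clinical investigation are informed that they can switch back to their usual mask if required".
- 13.5, after advice on side effects that intrude on daily life or prevent therapy: "Alternatively, participants can switch back to using their usual mask for PAP therapy".

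Section 12.1 describes the objectives as confirmatory. It scores each participant as meeting or not meeting each requirement, then tests each proportion against a reliability limit with a one-sided test at 0.05. On purpose, section 5.4 says: "This clinical investigation is designed to validate and confirm the overall performance and acceptability of the" mask (its name is blacked out).

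**The concern.** Acceptability is part of what the study sets out to confirm. A participant who gives up the mask because it hurts, leaks or causes side effects has shown that it was not acceptable to them. That is an outcome. The exclusion in 12.4 treats it in the same way as non-use with no connection to the mask, such as illness or travel.

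If such participants are removed, the pass proportion describes only people who tolerated the mask, and it is still compared with a limit meant for everyone fitted. Section 10.2 states that there is no control group, so no second arm shares the distortion. With 40 to 45 participants (section 9.6), moving two or three people out of the denominator can matter to a single requirement.

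**Working it through.** **No figure to reproduce.** The visible text gives no reliability limit, expected pass rate, abandonment rate or sample-size derivation. What follows is an illustration.

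**Inputs.** From the documents: N = 40 (lower end of the range in 9.6), one-sided test with P ≤ 0.05 to pass (12.1). Assumed: the limit R, the counts, and that the one-proportion test is the exact binomial.

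**Formula.** For k passes among n participants, p = Σ from x = k to n of C(n,x) R^x (1−R)^(n−x).

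**Scenario.** 40 fitted; 34 meet the requirement; 3 use the mask and do not meet it; 3 abandon it for a mask-related reason but stay enrolled. Counted as not met, the result is 34/40 = 85.0%. Excluded, it is 34/37 = 91.9%.

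| Assumed R | p, 34/40 | p, 34/37 | Verdict |
|---|---|---|---|
| 0.70 | 0.024 | 0.001 | passes both ways |
| 0.75 | 0.096 | 0.009 | fail becomes pass |
| 0.80 | 0.286 | 0.045 | fail becomes pass |
| 0.85 | 0.607 | 0.174 | fails both ways |
| 0.90 | 0.900 | 0.486 | fails both ways |

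The count matters as well. At R = 0.80, 34 is the smallest number of passes out of 37 that succeeds (33/37 gives p = 0.112). Other counts reverse at other limits, again with 3 abandoners among 40:

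- R = 0.70: 31/40 gives p = 0.196 and 31/37 gives p = 0.044.
- R = 0.90: 37/40 gives p = 0.423 and 37/37 gives p = 0.020.

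So a reversal is possible at low and high limits alike, but only for results close to the pass boundary.

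**Type I error.** Suppose the true pass proportion among all fitted participants equals R, a fraction q abandon the mask, and every abandoner is a true failure. Among those retained the pass proportion is R/(1−q). At R = 0.80 that is 0.80/0.95 = 0.842 for q = 5% and 0.80/0.90 = 0.889 for q = 10%. Averaging over the random number retained from N = 40, the chance of a false pass is:

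- 0.029 if abandoners count as not met;
- 0.116 if they are excluded and q = 5%;
- 0.303 if they are excluded and q = 10%.

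The values of q are assumptions. This is also the worst case, since it takes every abandoner to be excluded.

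**The case against.** **A brief user may not be excludable at all.** Someone who wore the mask for a night has used it, so the default inclusion in 12.4 arguably covers them, and the exception could be meant only for people with no on-mask data. This stands in part. A reader might infer that the plan requires abandoners to be removed, or encourages abandonment. The text does neither: it informs participants that they may switch, and it permits an exclusion. But it does not say how much non-use qualifies, and it leaves that judgement to be made in an unblinded study.

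**The rule has a legitimate use.** AHI and leak come from the participant's own therapy device for all nights from Visit 1 (10.3). Nights on the usual mask would otherwise be credited to the investigational mask, and the reference in 12.4 to excluded data points may mean just this. That stands, and it is why AHI and leak need different handling. It also means that the bias need not always favour the mask: usual-mask nights could have scored as met.

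**The governing criteria are not visible.** Sections 9.1 to 9.5 show headings only, and the criteria announced in 12.2 do not appear. A rule for switching back could sit there, so a reader should not infer that the full plan has none. What can be said is that 12.4, the general rule on the analysis set, refers to no such exception.

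**Exclusions are documented, and section 11.2 records reasons for discontinuation.** These steps make the problem detectable, but they set no scoring rule. Section 11.2 concerns leaving the investigation, so it does not clearly reach someone who changes mask and stays enrolled.

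**Participants are established users.** Section 9.7 requires at least 3 months on a nasal pillows mask and compliance with therapy, so abandonment may be rare. The documents give no rate either way.

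**Conclusion.** The concern holds in a limited form. As written, 12.4 permits a participant whose non-use was caused by the mask to be dropped from a confirmatory pass proportion, and no visible text scores that participant as not met. For acceptability requirements the tendency is in the mask's favour.

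Its size cannot be taken from the documents. A reader might infer from the 80% example that the exclusion generally turns failures into passes. It does not: with the same 34 passes the verdict is unchanged at 70%, 85% and 90%. The example shows that three people can decide a requirement when the result lies near the boundary. It rests on an assumed limit, assumed counts and an exact binomial test. The change is worth making because the rule bears on a pass or fail conclusion and the correction is a matter of wording.

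**What to change.** Amend 12.4 as follows:

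1. **Acceptability requirements:** keep every participant fitted with the investigational mask in the denominator. Score as not met anyone who stops using it for a mask-related reason (discomfort, leak, side effect, malfunction).
2. **AHI and leak requirements:** exclude only the nights on the usual mask and score on the investigational-mask nights. Count as not met a mask-related stopper with too few such nights to score. Failing such a person on every requirement would over-correct, because 12.1 tests each requirement separately and they may have met AHI or leak while using the mask.
3. **Whole-participant exclusion:** allow it only for non-use unrelated to the mask, with the reason documented.
4. **Definitions:** state in advance what counts as non-use (whole or partial period) and the minimum number of nights needed to score.
5. **Reporting:** give each requirement with and without exclusions.

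This changes the analysis only; what participants are told about returning to their usual mask is untouched. The cost is a few sentences, a recorded reason for stopping for participants who stay enrolled, and a record of which mask was used on which nights if the blacked-out procedures do not already provide one. Pass proportions may come out slightly less favourable.

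### In the readable text, sections 12.4 and 10.12 make withdrawn participants' data optional and conditional on being complete, so a mask-related failure can leave the denominator without a plan deviation

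*Combined protocol and SAP*

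**What the plan says.** Section 12.1 scores each participant as meeting or not meeting each requirement. It then applies a one-sided one-proportion test per requirement against a reliability limit, passing at P ≤ 0.05. It describes the objectives and endpoints as confirmatory and as supporting regulatory clearance.

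Section 12.4 sets the default: "Data from all participants who use the investigational product as part of this clinical investigation will be included in the analysis", unless there is a clear reason to exclude. The one example is "such as definitive proof the participant was not using the investigational product during the intervention period". Exclusions must be documented with a reason. For withdrawn participants the wording becomes permissive: "all data collected up to the point of withdrawal may be used in the analysis, provided the data is complete and accurate".

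Section 10.12 repeats the permissive rule ("Data from withdrawn participants may be used when results of the clinical investigation are analyzed if it is complete and accurate") and begins a sentence on the alternative, "If data from withdrawn participants is not used", whose ending is redacted. It also says that participants may withdraw "without prejudice or compromise to their medical care, and are not obliged to state their reasons".

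Section 11.2 requires reasons for withdrawal to be recorded. It foresees discontinuation linked to the mask's performance or safety, with follow-up where possible, but does not say how such a participant is scored.

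**The concern.** In a single-arm test of a proportion, the denominator helps decide pass or fail. People who leave early are the most likely to have incomplete data, and some may leave because the mask did not work for them. If their data are judged incomplete and left out, failures are removed and the observed pass proportion rises.

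The safeguards make this visible but do not prevent it. Documentation under 12.4 records an exclusion without fixing the analysis set in advance. Section 12.3 asks for deviations from the statistical plan to be explained, but leaving out an incomplete withdrawn participant follows the plan. The recorded reason cannot settle every case, because participants need not give one. The study is unblinded (10.2), so the decision could be taken with the outcome known.

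At stake is whether a stated 5% one-sided error holds for a confirmatory pass/fail claim.

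**Working it through.** **Inputs from the plan.** One-sided test, pass if P ≤ 0.05 (12.1); 40 to 45 participants (9.6); no replacement once all original recruits have attended their first appointment (10.12), so a later exclusion shrinks n. The readable text gives no reliability limit, withdrawal rate or power, so there is no planned figure to reproduce.

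**Assumptions.** Limits p0 = 0.70, 0.75, 0.80, 0.85, 0.90; n = 40 and 45 (10 cells); exact binomial test; true pass proportion equal to p0; every leaver excluded, although the text permits their use.

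**Formulas.** P-value for s passes in n: P = Pr[Bin(n, p0) ≥ s]. The number of failures is Bin(n, 1 − p0). The test is repeated on those remaining, and the false-pass rate is the total probability of samples that then reach P ≤ 0.05. With overall leaving rate L and a share q of leavers being failures, each failure leaves with probability L·q/(1 − p0) and each success with probability L·(1 − q)/p0. For unrelated leaving, both probabilities equal L.

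**False-pass rate (%).**

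| n | p0 | All kept | One failure dropped | Unrelated, L = 5% / 10% | L = 5%, q = 0.5 | L = 5%, q = 0.75 |
|---|---|---|---|---|---|---|
| 40 | 0.70 | 2.38 | 5.53 | 3.24 / 3.19 | 4.35 | 6.19 |
| 40 | 0.75 | 4.33 | 4.33 | 2.77 / 3.23 | 4.09 | 5.94 |
| 40 | 0.80 | 2.85 | 7.59 | 3.41 / 2.89 | 5.53 | 8.10 |
| 40 | 0.85 | 4.86 | 4.86 | 2.10 / 2.24 | 4.03 | 6.30 |
| 40 | 0.90 | 1.48 | 8.05 | 1.84 / 2.30 | 4.42 | 7.57 |
| 45 | 0.70 | 4.71 | 4.71 | 3.41 / 3.42 | 4.65 | 6.72 |
| 45 | 0.75 | 4.46 | 4.46 | 2.96 / 3.13 | 4.47 | 6.60 |
| 45 | 0.80 | 3.82 | 9.02 | 2.83 / 2.78 | 4.79 | 7.24 |
| 45 | 0.85 | 2.65 | 7.85 | 3.44 / 3.37 | 6.62 | 10.28 |
| 45 | 0.90 | 0.87 | 5.24 | 1.12 / 1.44 | 2.99 | 5.48 |

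Reading the columns:
- Unrelated leaving never exceeds 5%.
- With 5% leaving (about two people) and half of them failures, 2 of 10 cells exceed 5%.
- With three quarters failures, all 10 do. That is strong selection: at p0 = 0.90 it means 0.05 × 0.75 / 0.10 = 37.5% of all failures leave and are excluded.
- Dropping one failure changes nothing in 4 of 10 cells.

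**Single results.** At p0 = 0.80, 40/45 gives P = 0.090 (fail); without one failure, 40/44 gives P = 0.044 (pass). Reversal is not automatic: at the same limit, 34/40 (P = 0.286) still fails after two failures are dropped (34/38, P = 0.099).

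**The case against.** The strongest reply is that inclusion is the default. Someone who tried the mask and stopped is naturally a user, and the only exclusion example concerns proven non-use. The withdrawal sentence can be read as extending inclusion to partial data. This has force: a reader might infer that the plan excludes withdrawn participants, and it does not say so. What remains is that the sentence specific to withdrawals is permissive and conditional, so it leaves open what the default appears to settle.

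Second, redaction falls where an answer could sit: after the words on unused data in 10.12, and in 9.3, 9.5 and 12.2. A definition of completeness or a failure-scoring rule may be there. A reader might infer that the plan has no such rule; the documents do not support that, and the point is limited to the readable text.

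Third, exclusions and reasons are recorded, device data are downloaded for all nights from Visit 1 (10.3), and participants are told that "they can return to using their usual mask for PAP therapy during the clinical investigation if they have reason to do so", so a poor experience need not produce a withdrawal or lose all data. These points reduce the likely size but do not fix the denominator.

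Finally, the limits, leaving rate and share of failures are all assumed. That stands.

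**Conclusion.** The point holds for the readable text. The two statements in 12.4 do not settle whether a withdrawn user must be counted, and following the withdrawal rule as written can remove mask-related failures from the test without a deviation. It should be fixed before results are seen; confidence is medium because of the redactions.

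The size is conditional. Under the stated assumptions, the false-pass rate moves from 0.9%–4.9% with everyone kept to 3.0%–6.6% when 5% leave and half are failures. It reaches 5.5%–10.3% only under strong selection. If leaving is unrelated to outcome, it stays at 1.1%–3.4%. A reader might infer that this trial's error rate exceeds 5%. The documents do not support that: the actual limits and withdrawal rate are unreadable, and every scenario excludes all leavers, which the plan permits but does not require.

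**What to change.** In 12.4 and 10.12:

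1. Define the primary analysis set as every participant fitted with the investigational mask, stating that someone who tried it and stopped is a user.
2. Replace the permissive wording with a statement that withdrawn participants' data *will be used*. Drop completeness as a condition, keep the accuracy check, and keep any requirement result validly scored before withdrawal.
3. Where a requirement result is missing and the recorded reason is poor performance or safety of the mask, count every such missing result as not met in the primary test.
4. For results missing for other or unstated reasons, use available data in the primary test and report a sensitivity analysis with all missing results counted as not met.

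If the redacted text already holds a rule, align both sections with it instead.

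**Cost.** The change is to wording; the fix itself requires no added visits or participants. The pass proportion becomes slightly less favourable, and the chance of passing can fall materially. At an assumed limit of 0.80, a pass needs 37/40 or 41/45. With a true pass probability of 0.95, one imputed failure has this effect:

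- n = 40: Pr[Bin(40, 0.95) ≥ 37] = 86.2% becomes Pr[Bin(39, 0.95) ≥ 37] = 69.1%.
- n = 45: Pr[Bin(45, 0.95) ≥ 41] = 92.7% becomes Pr[Bin(44, 0.95) ≥ 41] = 82.3%.

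At an assumed limit of 0.90, a pass needs 40/40 or 45/45, so a single imputed failure prevents it (39/40, P = 0.0805; 44/45, P = 0.0524). The sponsor should check the planned size against the actual limits when adopting the rule.
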